Studies suggest that errors made during training improve later performance of the task. For example, in a study in which elderly subjects practiced rhythmic motion of the upper limb with and without visual feedback, greater errors made during treatment led to more movement improvement following training (Levy-Tzedek 2017). This result is consistent with the TCT as muscle activation is regulated by the difference between the actual limb position and referent limb position specified by the brain. The referent position also plays a role in the perception of the actual limb position, while the afferent component identifies the deflection of the limb from the referent limb position. Based on this combination, the system identifies the movement error, i.e., deviation of the limb from the target position. Movement correction is accomplished by properly adjusting the referent limb position.

The sensitivity of referent control may be enhanced by augmentation of the movement error, i.e., Joint Error Augmentation (JEA). Furthermore an improvement in referent limb control is likely to be associated with improvement in threshold (referent control) at the level of individual joints. Development of rehabilitation treatment protocols based on motor control theory, such as that underlying JEA, is a promising direction for robotic rehabilitation therapy.

Research Objectives:

Our goals are to investigate the effect of JEA on motor learning in healthy subjects and on upper limb rehabilitation in subjects with stroke.

Hypothesis 1: In both groups, JEA applied to the elbow joint range will lead to better learning of movement speed and precision of a reaching task compared to no JEA.

Hypothesis 2: In patients with stroke, JEA applied to the elbow joint range will lead to a greater increase in the patient's active control zone at the elbow compared to no JEA and thus in his/her ability to perform isolated voluntary movement of the elbow.

Research plan

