In our preliminary proof of principle study, we developed and tested a passive robotic system in 21 healthy subjects (aged 26.2, SD 1.2 yrs). A passive robotic arm was developed for supporting and monitoring arm motion and combined with a simple virtual reality pick-and-place game (Srör et al. 2018). Software was developed for integrating input from the robotic arm and a Kinect camera. The software includes a pick-and-place VR game, game success feedback, and motion feedback with and without JEA. Individuals were assigned to a training group with or without EA and performed one 30 min training period. There was no difference between groups in terms of the success rate of hitting the targets. The group training with EA tended to work longer and be more motivated. The application was found to be acceptable to healthy individuals, to enhance motivation to exercise and not to cause fatigue or any adverse effects (Srör et al., 2018; 2019a; 2019b).

The next phases of the study are to investigate the effects on learning with JEA feedback in healthy subjects, and then to test the JEA feedback effect in patients with stroke.

In two separate studies, we will test 24 healthy subjects and 24 patients who have moderate-to-severe stroke (spasticity + some arm movement). Testing of the healthy subjects will be done in Canada and testing of patients will be done in two countries (Israel-Soroker Hospital, Beer-Sheva; Canada-Jewish Rehabilitation Hospital, Laval/Montreal). The motivation for testing the application in patients at two sites is to assess the feasibility of conducting a multi-site study using this technology.

In both studies: Subjects will be randomly allocated to two equal groups. One group (control) will receive regular feedback and the other group will receive JEA feedback (randomized with catch trials).

Subjects will perform ~30 min of target reaching with their non-dominant/affected arm, 3 times in one week, with a minimum of 1 day between sessions. Rest periods will be provided when needed to avoid subject fatigue. In the experimental group, target locations will be tailored to coincide with active control range limits determined at the beginning of each session. In the stroke group, workspace extensions will be added as active range increases (i.e., exercise progression) for patients receiving JEA feedback.

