Session 1 (1 hour and 15 min) will include a Reaching Pre-Test of 10 trials to a fixed target (see below), reaching training and evaluation of perceived exertion. Session 2 (1 hour) will include the evaluation of the TSRT in the stroke group, reaching training and perceived exertion rating. Session 3 (2 hours) will be the same as Session 2 but the last 10 trials of Session 3 will be done to a fixed target (Post-Test). Following Session 3, there will be a pause of 1 hour after the training and then a Reaching Follow-up Test of 10 trials to a fixed target will be done. In addition, the stroke group will undergo a clinical evaluation including determination of the elbow flexor TSRT angle prior to Session 1 and another clinical evaluation following Session 3.

For Study 1, the primary outcome measures are change in the index of performance (IP), which is a measure of reaching efficiency (Takeda et al., 2019).

For Study 2, the primary outcome measures are the same as those for the healthy group as well as the area of the active control workspace based on the TSRT and spasticity. The **secondary outcome measures** are the change in the FMA-UL and patient effort according to the Borg scale.

Evaluations for Study 2:

Clinical evaluation sessions: Clinical assessments will be conducted by a blinded assessor before (Pre-test) and after (Post-test) the last training session. In the Pre and Post-test sessions, all of the following assessments will be done.

Arm motor impairment: **i) Voluntary arm motor ability and coordination** will be evaluated using the valid (Berglund and Fugl-Meyer 1986) and reliable Fugl-Meyer Arm Assessment (FMA; Fugl-Meyer et al. 1975) that measures reflexes, volitional movements and UL

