coordination on a 66 point scale. FMA also evaluates sensation (light touch), kinaesthesia and passive range of motion on ordinal scales; **ii) spasticity** will be measured by the Modified Ashworth Scale (Bohannon and Smith 1987) on a scale of 0 to 4 ; **iii) TSRT** The *threshold of the active control zone* of the elbow will be identified by determining the tonic stretch reflex threshold (TSRT) angle in elbow flexors using the Montreal Spasticity Measure (Calota et al. 2008). This methodology has been successfully implemented in our previous RCT ([name] et al. 2018). It consists of recording electromyographic signals from the elbow flexors and extensors with surface electrodes as well as the elbow angle using a goniometer, while the elbow is stretched from flexion to extension 20 times. Then, determination of the active control workspace will be done by passively moving the arm attached to the robot arm at a moderate speed throughout the horizontal workspace while monitoring elbow extensor and flexor EMG on an oscilloscope and respecting the identified elbow joint range limitation. Since, no EMG activity should be present at rest, the appearance of elbow flexor or extensor activation during passive manipulation of the arm through the horizontal shoulder/elbow workspace will indicate that the elbow has been moved beyond the TSRT angle. In this way, the TSRT angle will define the limits of the whole arm active control workspace. The area of the active control workspace will be computed from the x, y workspace recorded by the Kinect II camera using enhanced tracking and expressed as a percentage of the full biomechanical workspace defined by the limits of the passive shoulder horizontal/elbow area.

Fig. 1. Training position and set-up.

For both studies: Training protocol (Fig 1): As described above, the arm active control workspace will be measured by the Kinect II camera and reproduced in the VR workspace for each session. Objects to be reached will be displayed within this defined VR workspace for both groups. In this way, the training will be personalized to the range of active motion in each subject. Three 30 min training sessions will be done. At the end of each training session, the patient's perceived *sense of effort* will be evaluated with the valid and reliable 20 pt Borg Rating of Perceived Exertion Scale (Borg 1982).

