To address Hypothesis 2, changes in the area of the active control workspace and clinical scores will be compared between groups using paired t-tests after verifying for data normality.

Knowledge translation

The preliminary results will primarily be used to inform the design of a full randomized controlled trial. However, preliminary results will be shared with clinicians at both sites and by oral or poster presentations at local, national or international meetings.

Participating researchers

[name] is a 1st year Master's student in the Integrated Program of Neuroscience at McGill University. **[name]** is Professor in the School of Physical and Occupational Therapy in the Faculty of Medicine at McGill University. She has pioneered many innovations in the area of upper limb rehabilitation, including identification of underlying motor control deficits at the joint and interjoint level, measurement of spasticity, incorporation of VR training interventions and the distinction between compensation and recovery. **[name]** is an Associate Professor in the Department of Industrial Engineering and Management at Ben-Gurion University of the Negev. She leads the Telerobotics laboratory where robotic motion control, learning, and interaction methodologies are developed and assessed. [name] has applied advanced mathematical methods for modeling and analysis of arm motion in healthy subjects and in patients with stroke. **[name]** is a Senior Lecturer in the Department of Physiotherapy who has been studying human movement in health and in disease for over a decade, publishing in journals that are either specific to neurological rehabilitation, or appropriate for inter-disciplinary research (e.g., in *Scientific Reports*). Profs. [name] and [name] have been collaborating on stroke rehabilitation for close to a decade. They have jointly published papers in leading journals and conferences [e.g., 15-17] and have worked together in two funded research projects. [name] and [name] have collaborated on robotic rehabilitation, and have jointly supervised a student working on robotic mirror-game treatment [18].

Budget and matching funds: details and justification

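### Hypothesis 2 rests on an unadjusted workspace change with no follow-up measure, and the workspace values taken before Sessions 2 and 3 have no specified analysis

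*Combined protocol and SAP*

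**What the plan says.** Under Research Objectives, Hypothesis 2 predicts that "JEA applied to the elbow joint range will lead to a greater increase in the patient's active control zone at the elbow" than training without JEA. It names no time point and makes no claim about persistence. The Research plan lists the TSRT-based workspace area among the Study 2 primary outcomes. Evaluations for Study 2 expresses that area as a percentage of the full biomechanical workspace.

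The Data analysis section gives the whole analysis in one sentence: "changes in the area of the active control workspace and clinical scores will be compared between groups" by paired t-tests, after a check of normality. No time points are named. The clinical assessments are made by a blinded assessor "before (Pre-test) and after (Post-test) the last training session". The session description has one clinical evaluation prior to Session 1 and "another clinical evaluation following Session 3", with no stated delay after training. The Follow-up one hour after Session 3 consists of ten reaches to a fixed target and serves the IP analysis.

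Measurements are also made between these two evaluations. "Session 2 (1 hour) will include the evaluation of the TSRT in the stroke group", and Session 3 repeats the content of Session 2. In the Training protocol, "the arm active control workspace will be measured by the Kinect II camera and reproduced in the VR workspace for each session". The description of the robotic system places the determination of active range before each training session in the stroke group. Sessions take place "3 times in one week, with a minimum of 1 day between sessions".

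**The concern.** For IP, the plan distinguishes improvement (Pre-Test to Post-Test) from learning (Post-Test to Follow-Up). The workspace, which is the direct test of Hypothesis 2, gets no such distinction. If the Post evaluation falls soon after Session 3, a brief shift in the reflex threshold and a gain that survives to another day would look the same. The plan does not say when that evaluation takes place.

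The session-start values bear on part of this question because at least a day without training precedes them. As written, they set up the game and have no further role. The results are meant primarily to inform the design of a full randomized trial, where carry-over from session to session is useful to know.

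The test is a second weakness. A paired t-test does not fit a comparison of two independent arms. A plain change score also makes less efficient use of the baseline than adjustment does, which matters with 12 patients per arm.

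**Working it through.** **1. Text check.** The plan states no alpha, power, SD or effect size for this outcome, so there is no figure to reproduce. The occasions compare as follows.

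| Occasion | TSRT/workspace measured? | Analysis specified? |
|---|---|---|
| Clinical evaluation before Session 1 | Yes | Yes (inferred; time points not named) |
| Start of Session 2 | Yes, 1 day or more after Session 1 | No |
| Start of Session 3 | Yes, 1 day or more after Session 2 | No |
| Clinical evaluation after Session 3 | Yes, delay not stated | Yes (inferred) |
| One-hour Follow-up | No, reaching only | Not applicable |

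**2. Gain from baseline adjustment.** Inputs: 12 per arm (Data analysis). Assumed: equal SD (set to 1) at all occasions and equal correlation r between them, with r = 0.5 to 0.9.

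- Variance per patient of a change score: 2(1−r).
- Variance per patient after baseline adjustment: 1−r².
- Ratio: (1−r²)/[2(1−r)] = (1+r)/2.

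| r | Change score | Adjusted | Ratio | Reduction |
|---|---|---|---|---|
| 0.5 | 1.00 | 0.75 | 0.75 | 25% |
| 0.7 | 0.60 | 0.51 | 0.85 | 15% |
| 0.9 | 0.20 | 0.19 | 0.95 | 5% |

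These are large-sample values. Estimating the baseline slope from 24 patients inflates the adjusted variance by about 1 + 1/(24−4) = 1.05. The ratios become 0.75 × 1.05 = 0.79 and 0.95 × 1.05 = 1.00, so at r = 0.9 the gain is about nil.

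**3. What the two extra occasions add to the Post contrast.** The model has a common baseline, free arm-by-session terms and complete data. The generalised least squares variance of the Post contrast is (2/12)(1−r²).

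- r = 0.5: 0.125 with four occasions, 0.125 with Pre and Post only.
- r = 0.9: 0.0317 with four occasions, 0.0317 with Pre and Post only.

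The gain is 0%. Every post-baseline occasion has the same regressors (baseline and arm), so the other occasions carry no further information about the Post effect.

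**4. Precision of the Session 3-start contrast.** Under the same assumptions its standard error is √[(2/12)(1−r²)], which is 0.354 SD at r = 0.5 and 0.178 SD at r = 0.9. With a t multiplier of 2.08 (21 df), the 95% half-width is 2.08 × 0.354 = 0.74 SD and 2.08 × 0.178 = 0.37 SD.

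**5. Agreement in sign as evidence of persistence.** Under the same assumptions the Session 3-start and Post contrasts correlate at (r−r²)/(1−r²) = r/(1+r), which is 0.33 to 0.47. Suppose there is no true effect at the start of Session 3. Given a significant positive Post result (z > 1.96, normal approximation), the Session 3-start contrast is also positive this often:

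- 60% to 65% of the time if the true Post effect is 2 standard errors;
- 79% to 89% of the time if there is no Post effect either.

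**The case against.** The best defence is that Hypothesis 2 predicts a greater increase and does not claim that it lasts. A Pre/Post comparison matches that wording, and the study is preliminary. This stands: the plan has a gap but does not contradict itself. The Data analysis section also names no time points, so the fair statement is that no analysis of the session values is specified. It does not follow that they will be thrown away.

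Three stronger readings are tempting, and the documents do not support them.

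- *A reader might infer that the session values show whether the gain lasts.* The start of Session 3 precedes the last training. It reflects two of the three sessions and cannot show retention after the full course. Nor do agreeing signs support a lasting effect, as step 5 shows.
- *A reader might infer a large gain in precision from four occasions.* Gains of 11–13% (effect growing linearly) or 54–80% (full effect after Session 1) can be calculated under equal correlation. They require a single treatment parameter with a known shape over sessions. The plan gives no such shape, and with free session terms the gain is nil.
- *A reader might infer that usable values already exist for every patient at no cost.* The Training protocol has the workspace measured for each session and objects shown within it in both groups. The Research plan, however, ties session-start tailoring of targets to the experimental group. The robotic-system text describes an elbow range, not an area, and the difficulty rules move targets by active range in one arm and by fixed 2 cm steps in the other. No text says that percentage area is computed at each session.

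Blinding also counts against giving these values the lead. A blinded assessor is specified for the clinical evaluations, and evaluators are said in general to be blinded. Who takes the session-start values is not stated.

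**Conclusion.** The point holds as a gap in the analysis that should be closed. A primary outcome is apparently compared only as Pre-to-Post change, by a test that does not suit independent arms. It has no follow-up measure, and the interim values have no stated use.

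The benefit is modest. Baseline adjustment lowers the variance of the primary contrast by 25% to 5% for r = 0.5 to 0.9, or about 21% to 0% after the small-sample cost. This assumes equal SDs and equal correlation, neither of which the documents give. The session values add no precision to the Post contrast. They add an estimate of carry-over after two sessions, which the plan lacks, with a 95% half-width of about 0.74 to 0.37 SD. That estimate is supportive only.

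**What to change.** - **Primary analysis.** Keep the blinded Pre/Post between-arm contrast in percentage workspace area as primary. Estimate it in a mixed model with a common baseline and arm-by-session terms, in place of the paired t-test on changes. Name the time points.
- **Session values.** Save the Session 2 and Session 3 start values as percentage area, by the same procedure in both arms, and include them in the model.
- **Secondary estimate.** Report the Session 3-start arm contrast with its confidence interval as carry-over after two sessions. Do not call it retention after the full course, and do not claim a lasting effect because its sign agrees with the Post contrast.
- **Timing.** State the delay between Session 3 and the Post evaluation. Reconcile "before (Pre-test) and after (Post-test) the last training session", which can be read as placing the Pre-test before Session 3, with the evaluation described as prior to Session 1.
- **Reconciliation.** Reconcile the Research plan, the Training protocol, the robotic-system description and the difficulty rules on whether and how the workspace is measured each session in both arms. State who takes these values and whether they are blinded.

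No new visit is needed. The cost is revised analysis wording, a common measurement procedure and the saving of the values. The downside is that the session values may be unblinded, which is why they stay secondary.

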calculations of Kalman gains for elbow and wrist also account for shoulder and elbow error covariance respectively. Segment lengths are updated after each measurement step. Objects to be reached in VR are determined before training based on the subject's arm range of motion. The RANSAC algorithm (Fischler and Bolles 1981) is used to fit the recorded arm positions into the plane to reduce measurement errors.

Subjects and subject recruitment. Participants will be allocated by random numbers to either an *experimental group* that will receive JEA feedback (randomized with catch trials) or a *control group* that will receive no JEA feedback. **Blinding:** The sequence of allocation will be concealed from those assigning participants to groups until the moment of assignment, to prevent them from consciously or unconsciously influencing which participants are assigned to which groups. Participants will also be blinded to group allocation. Finally, evaluators will be blinded by concealing participant group allocation.

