Patients will be recruited through well-established procedures at the JRH. Potential participants will be identified from chart or database review and sent a letter of information describing the study. If they are interested, they will be directed to contact the research assistant by phone or email who will schedule them for a screening interview. Healthy subjects will be recruited from the community with the help of information flyers posted on bulletin boards. Subjects will participate after signing informed consent forms approved by the Center for Interdisciplinary Research in Rehabilitation (CRIR) Ethics Committee. Handedness will be measured for both studies with the Edinburgh Handedness Inventory (Oldfield 1971) but for Study 2, both right- and left-handed subjects will be included since hemispheric dominance is not expected to influence results. For Study 1, healthy women and men will be included who 1) are between the ages of 18-75 yrs; 2) have normal or corrected-to-normal vision; and 3) are able to provide informed consent. For Study 2, women and men will be included who 1) sustained a first cortical/sub-cortical ischemic/hemorrhagic stroke <1 yr previously and are medically stable; 2) are aged 18-75 yrs to minimize confounding effects of age-related changes in muscular responses; 3) are no longer receiving treatment; 4) have arm paresis (Chedoke-McMaster Arm Scale of 2-6 /7; Gowland et al. 1993) but are able to perform voluntary elbow movement of at least 30° per direction; 5) have mild-moderate elbow flexor spasticity; and 6) are able to provide informed consent. Subjects will be excluded if they have/are: 1) other major neurological neuromuscular/orthopaedic/pain problems that may interfere with task performance; 2) major cognitive deficits (<26 on Montreal Cognitive Assessment; Nasreddine et al. 2005) or 3) depression (> 14 on Beck Depression Inventory II; Beck et al. 1988; 1996).

[figure not shown]

Fig. 3. UL model based on the Kinect II skeleton (left) and explanation of the extended Kalman filter (right) to improve motion tracking accuracy.

Data analysis

For Study 2, data from Canada will be combined with those from Israel for a total of 12 subjects per group.

To address Hypothesis 1, we will compare the change in the IP between the Pre-Test and the Post-Test as an indicator of motor improvement and the change from Post-Test to Follow-Up as an indicator of motor learning using paired t-tests after verifying for data normality.

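### Paired t-tests are the only tests named for comparing two independent randomised groups; for Hypothesis 1 no comparison between groups is stated

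*Combined protocol and SAP*

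**What the plan says.** Both hypotheses under Research Objectives contrast the two treatments. Hypothesis 1 states that JEA "will lead to better learning of movement speed and precision of a reaching task compared to no JEA". Hypothesis 2 predicts, in stroke patients, a larger gain in the elbow's active control zone "compared to no JEA and thus in his/her ability to perform isolated voluntary movement of the elbow".

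The design is parallel-group. The Research plan says of both studies: "Subjects will be randomly allocated to two equal groups". Under Subjects and subject recruitment: "Participants will be allocated by random numbers to either" an experimental or a control group. For Study 2, "data from Canada will be combined with those from Israel for a total of 12 subjects per group". Matching, pairing and crossover are not mentioned.

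The Data analysis section has one sentence per hypothesis:

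- Hypothesis 1 is to be addressed as follows: "we will compare the change in the IP between the Pre-Test and the Post-Test as an indicator of motor improvement". A second interval, which starts at the Post-Test and ends one hour later, is to be used "as an indicator of motor learning using paired t-tests after verifying for data normality". The treatment group is not mentioned.
- Hypothesis 2: changes in workspace area and clinical scores "will be compared between groups using paired t-tests after verifying for data normality".

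No other test or model appears in the document.

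**The concern.** A paired t-test needs a defined partner for each observation. Two arms of different people, individually randomised, supply none. For Hypothesis 2 the sentence already takes change as the data and says that groups are compared, so it cannot be read as a within-person test. The analyst would have to invent pairs, and the p-value and confidence interval would then depend on the order of the rows.

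The Hypothesis 1 sentence is ambiguous. Read as tests across time within people, it is a legitimate paired analysis of the wrong question: whether performance changed, not whether JEA changed it more. Read as a comparison of change between arms, it has the right target and the same wrong test as Hypothesis 2. Either way it needs correcting.

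Change in IP is the primary outcome of Study 1 and one of the primary outcomes of Study 2, and workspace area is another in Study 2, so the defect reaches the main comparison of both studies. Knowledge translation says the results will mainly feed the planning of a full-scale randomised trial. That planning needs the JEA-minus-control difference and its precision.

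**Working it through.** **Inputs.** 12 per arm: 24 in each study, split equally; stated directly for Study 2. The plan gives no alpha, effect size, SD or dropout figure. Assumed here: two-sided alpha 0.05, normal data, and a range of effects. Let d be the JEA-minus-control difference in mean change, in SDs of change. The plan reports no power figure to reproduce.

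**Hypothesis 2, pairs formed without regard to outcome.** Independent people are uncorrelated, so the SD of a within-pair difference is SD × √2. The noncentrality is (d/√2) × √12 = d × √6, the same as for the two-sample test, d/√(1/12 + 1/12). Only the degrees of freedom differ: 12 − 1 = 11 (critical t 2.201) against 12 + 12 − 2 = 22 (critical t 2.074). Power from the noncentral t:

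| d | two-sample, df 22 | arbitrary pairs, df 11 |
|---|---|---|
| 0.5 | 22% | 20% |
| 0.8 | 47% | 43% |
| 1.2 | 80% | 76% |

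Simulated type I error of the arbitrary-pair test is 5.1% (100,000 data sets).

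**Unequal completers (assumed), d = 1.2.** The paired test keeps only as many pairs as the smaller arm has people.

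- 12 v 11: noncentrality 1.2/√(1/12 + 1/11) = 2.87 unpaired, (1.2/√2) × √11 = 2.81 paired; power 78% and 72%.
- 12 v 10: 1.2/√(1/12 + 1/10) = 2.80 unpaired, (1.2/√2) × √10 = 2.68 paired; power 76% and 67%.

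**Row order.** Simulated data sets were shifted to have a given unpaired p, then re-paired at random (200 data sets per p, 4,000 re-pairings each):

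| unpaired p | orderings with paired p < 0.05 |
|---|---|
| 0.005 | 100% |
| 0.02 | 84% |
| 0.04 | 48% |
| 0.06 | 27% |
| 0.10 | 10% |
| 0.20 | 1% |

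If rows happened to be sorted within each arm by a variable correlated 0.5 or 0.7 with the change, type I error would be 8% or 13%. Sorted by the change itself, it would be about 52%. The plan describes no such sorting.

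**Hypothesis 1, within-group reading.** For a gain of g SDs in an arm of 12, the noncentrality is g × √12 with df 11; call the power p. Suppose JEA adds nothing, and a result significant in the JEA arm but not in control is taken as a JEA effect. The chance of that is p(1 − p):

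| shared gain g | p | p(1 − p) |
|---|---|---|
| 0.3 | 0.158 | 13% |
| 0.5 | 0.353 | 23% |
| 0.62 | 0.500 | 25% |
| 0.8 | 0.714 | 20% |
| 1.0 | 0.883 | 10% |
| 1.2 | 0.965 | 3% |
| 1.5 | 0.997 | 0.3% |

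Now let JEA truly add 1.2 SD. The rule succeeds with probability p(JEA) × (1 − p(control)). At control gains of 0.3, 0.5, 0.8 and 1.0 SD that is 84%, 65%, 29% and 12%. For example, at 1.0 SD the JEA arm's power is close to 1, so the chance is about 1 − 0.883 = 0.117. A two-sample test has 80% power whatever the shared gain. If both arms were pooled over time (24 people), a gain of 0.5 SD would be detected with 65% power and the result would say nothing about JEA.

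**The case against.** The strongest defence is that *paired* is a slip for *unpaired* and would surface at analysis, because standard software will not pair two groups of different people unless someone builds the pairs. For Hypothesis 2 this may be so. But the word stands in both analysis sentences, nothing else in the document corrects it, and changing it would still leave Hypothesis 1 without an explicit comparison of arms.

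It can also be said that Hypothesis 1 is defined against no JEA, and that comparing *the change* naturally means comparing it between arms. That is a fair reading, and on it Hypothesis 1 has only the same wrong test as Hypothesis 2. The sentence still does not say so.

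On harm, several points stand:

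- With 12 completers in each arm, arbitrary pairing leaves the estimated difference unchanged; only the p-value and interval move.
- Mean, SD and n of change by arm, if reported, would let a reader derive the difference and its standard error. The Data analysis section does not promise them.
- The sorted-row figures, the unequal-completer figures and the rule of significance in one arm only rest on events or practices that the plan does not describe. They show what the wording leaves open, not what will happen.

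**Conclusion.** The concern holds: the analysis is wrong as written and must be fixed. For Hypothesis 2 the named test does not exist for this design. For Hypothesis 1 the comparison that the hypothesis requires is not stated, and the only test named is unsuitable on one reading and answers a different question on the other.

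The conclusion follows from the text and does not depend on a large numerical bias. With outcome-blind pairs and equal arms, type I error stays near 5% and the power loss is about 2 to 4 percentage points over the effects tabulated. The main cost for Hypothesis 2 is a result that depends on row order, chiefly near the threshold. For Hypothesis 1 the cost is conditional on how within-group results would be read: up to 25% false claims with no JEA effect, and detection as low as 12% with a true effect of 1.2 SD, over the gains examined. These sizes assume two-sided alpha 0.05, normal changes with equal SD, and illustrative effects, since the plan gives none.

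**What to change.** Replace the paired t-tests in both Data analysis sentences.

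- **Hypothesis 1:** In each study, the change in IP from Pre-Test to Post-Test, and from Post-Test to Follow-Up, will be compared between the JEA and control groups with an independent-samples (Welch) t-test, reporting the JEA-minus-control difference with its 95% CI.
- **Hypothesis 2:** The same test and estimate for the Pre-test to Post-test change in active control workspace area and FMA, with a rank-sum test between groups for ordinal scores such as the Modified Ashworth Scale.

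State that these between-group comparisons are the primary analysis of each outcome. An ANCOVA adjusted for baseline, with site added in Study 2 because Canada and Israel are pooled, can be given as supporting only. Within-group paired t-tests can stay as description. The correction itself is the independent-samples comparison; Welch rather than Student and the supporting ANCOVA are recommendations. In simulation with 12 per arm, Welch held type I error at 4.9% and gave 80% power at d = 1.2, so nothing is lost by choosing it.

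The cost is two rewritten sentences and a line for the supporting and descriptive analyses. No new data or participants are needed. The change should be made before any outcome data are analysed, so that neither the reading nor the row order can be chosen afterwards.
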